Anaphylaxis	70/100,000 PY (in 0-19 yr olds, Minnesota, US) [Decker, 2008]	Monovalent measles (12 per 100,000 doses), MMR (1 per 100,000 doses), HPV bivalent (1.4 per million doses) or HPV quadrivalent (from 2.6 per 100,000 to 1.7 per million doses) [Vanlander, 2014] 0.65 (95% CI: 0.21, 1.53) per million doses for the most common vaccines for children and adolescents [Bohlke, 2003]	0-48 hours [Bohlke, 2003]	BC

ADEM= Acute Disseminated Encephalo-Myelitis; AE = adverse event; AESI = adverse event of special interest; Hib = *Haemophilus influenza* type B; HPV = human papilloma virus; MMR = measles, mumps, rubella; PCV = pneumococcal conjugate vaccine; SJS= Stevens Johnson Syndrome; TEN = toxic epidermal necrolysis; NA = not available; PY = person years; RR = relative risk; VAERS = Vaccine Adverse Event Reporting System.

CONFIDENTIAL

115055 (EPI-MALARIA-002 VS AME)
Protocol Amendment 7 Final

9.2.5.2. Hospitalisations for an AE other than an AESI, meningitis, any malaria or severe malaria (including cerebral malaria)

These include all hospitalisations reported by the physician not due to an AESI (Section 9.2.5.1), or to meningitis (Section 9.2.5.3), or to any malaria or to severe malaria (including cerebral malaria) (Section 9.2.5.5).

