9.2.7.2.10. Record diagnosis

Record main diagnosis and any secondary diagnoses made by the physicians in the eCRF.

CONFIDENTIAL115055 (EPI-MALARIA-002 VS AME)
Protocol Amendment 7 Final**9.2.7.2.11. Record haemoglobin measurement**

For all hospitalised subjects, measurement of haemoglobin concentration, if available, at hospital entry will be recorded in the eCRF.

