9.3.1. *Co-primary endpoints*

In children living in the study area, prior to implementation of RTS,S/AS01_E:

- Occurrence of AESI (see Section 9.2.5.1 for definition).
- Occurrence of other AE leading to hospitalisation or death (see Sections 9.2.5.2 and 9.2.5.8 for definitions).
- Occurrence of aetiology-confirmed meningitis (see Section 9.2.5.3 for case definition).

9.3.2. *Secondary endpoints*

In children living in the study area, prior to implementation of RTS,S/AS01_E:

- Occurrence of probable meningitis (final classification) (see Section 9.2.5.3 for case definition).
- Occurrence of clinically suspected meningitis (final classification) (see Section 9.2.5.3 for case definition).
- Occurrence of meningitis cases identified at site level (first line laboratory) (see Section 9.2.5.3 for case definition).
- Occurrence of hospitalisation (including those attributed to an AESI, other AE, meningitis, or malaria) or death.

CONFIDENTIAL

115055 (EPI-MALARIA-002 VS AME)
Protocol Amendment 7 Final

- Occurrence of febrile convulsions during the 7-day period (Days 0-6) and 1-month period (Days 0-29) following administration of routine EPI vaccines (see Section 9.2.5.4 for case definition).
- Occurrence of two events used as surveillance quality indicators: abscess at injection site during the 7-day period (Days 0-6) following any routine vaccination and foot positional deformation (see Section 9.2.6 for case definitions).
- Occurrence of episodes of malaria using RDT and/or microscopy
 - Any malaria (including *P. falciparum* malaria) (see Section 9.2.5.5 for case definition).
 - Severe malaria (including *P. falciparum* malaria) (see Section 9.2.5.5 for case definition).
 - Cerebral malaria (see Section 9.2.5.5 for case definition).
- Occurrence of anaemia (see Section 9.2.5.6 for case definitions) at hospital entry among hospitalised children.
- Occurrence of hospitalisation
 - All causes and hospitalisations for any malaria (including *P. falciparum* malaria), severe malaria (including *P. falciparum* malaria) and cerebral malaria (see Section 9.2.5.7 for case definitions).
- Occurrence of death
 - All causes and malaria attributed deaths (including *P. falciparum* malaria attributed death) (see Section 9.2.5.8 for case definitions).
 - AE attributed deaths (see Section 9.2.5.8 for case definitions).

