### 6.9.2.2. Other AE leading to hospitalisation or death

Other AE leading to hospitalisation or death are those events different from the pre-defined AESI, meningitis and malaria. These AEs classified by MedDRA SOC and PT level for hospitalised cases will be **described**:

- According to PI diagnosis corresponding to the diagnosis at discharge **for progress report (see section 6.9.3.1) and interim analysis**,
- According to final diagnosis (external expert diagnosis or PI diagnosis if external expert diagnosis not available) **for interim and final analysis**.

*PTs will be grouped into medically relevant groups to provide aggregated incidence rates. Indeed, due to the varied reporting terminologies used, some related or similar medical conditions may be counted separately resulting in partial incidence rate calculation (e.g. bacterial pneumonia and pneumonia, iron deficiency anaemia and anaemia). A manual grouping will be done based on a review of all the MedDRA PTs by the Epidemiologists and a Physician.*

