### **7.2.3. Date of occurrence**

The dates of occurrence of events are defined as follows depending on the endpoint:

- Suspected or confirmed AESI and meningitis reported at hospital:
  - Onset date of event
- Suspected AESI and suspected meningitis reported during outpatient visit (see section [7.3](#) for worst case allocation sensitivity analysis):
  - Admission date at outpatient visit
- Other AE leading to hospitalisation or death:
  - Onset date of event if AE is the primary diagnosis
  - Admission date at hospital otherwise
- Suspected or confirmed malaria cases:
  - Onset date of event for hospitalised cases
  - Admission date at outpatient visit otherwise
- Death:
  - Date of death reported in study conclusion

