### **7.2.8. Management of consecutive visits and/or hospitalisations**

#### **7.2.8.1. AESI, Meningitis and other AE**

For cases reported at hospital, events in one subject with the same preferred term and with the same onset date or onset date + 1 day will be considered as the same event. In such case, they will contribute to several hospitalisations and one event.

*Remarks:*

1. For other AE leading to hospitalisation or death, if the AE is not the primary diagnosis the hospital admission date will be considered (indeed, the onset date is only available for primary diagnosis).
2. For meningitis a worst case allocation is applicable. In case two or more hospitalisations occurred for different protocol definitions of meningitis with the same onset date or onset date + 1, the event considered will be the worst according to the following order (starting from worst):
  - Bacterial confirmed meningitis / Aetiology confirmed meningitis

- Probable meningitis
- Clinically suspected meningitis
- Suspected meningitis without diagnosis done by the site yet (applicable for progress report)
- Suspected meningitis ruled out afterward

3. This rule is applicable if their onset dates are complete.

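### The SAP counts secondary diagnoses as other AEs leading to hospitalisation without excluding admissions due to malaria, an AESI or meningitis, although the protocol leaves those admissions out of this co-primary endpoint

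*SAP*

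**What the plan says.** **Protocol.** Section 9.3.1 makes other AE leading to hospitalisation or death a co-primary endpoint and refers to 9.2.5.2 and 9.2.5.8 for its definitions. Section 9.2.5.2 works at the level of the admission: "These include all hospitalisations reported by the physician not due to an AESI", nor to meningitis, "or to any malaria or to severe malaria (including cerebral malaria"). Section 9.2.5.8 handles deaths differently: there it is enough that an AE is listed as a contributing cause. Section 9.2.7.2.10 has sites "Record main diagnosis and any secondary diagnoses made by the physicians in the eCRF".

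**SAP.** Section 6.9.2.2 works at the level of the coded event: "Other AE leading to hospitalisation or death are those events different from the pre-defined AESI, meningitis and malaria". Section 7.2.3 then gives two dates of occurrence for this endpoint: "Onset date of event if AE is the primary diagnosis" and "Admission date at hospital otherwise". Section 7.2.8.1 repeats the rule for merging duplicates ("if the AE is not the primary diagnosis the hospital admission date will be considered") and explains that an onset date exists only for the primary diagnosis. Section 6.9.3.2 applies at-risk periods of 7 and 30 days to other AEs and computes post-vaccination rates only for the 10 most frequent groups. Section 9, on changes from the protocol, does not mention the definition of this endpoint.

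**The concern.** The two documents do not select the same events. The protocol asks why the child was admitted; the SAP asks whether a coded term is itself an AESI, meningitis or malaria. The difference shows in an admission for malaria that also carries another diagnosis. Under the protocol the admission is outside the endpoint. Under the SAP the other diagnosis is an event different from malaria, has a date, and is not removed by any stated rule.

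This rate is part of the safety baseline for EPI-MAL-003. Protocol 9.4.3 expects *P. falciparum* malaria to fall in vaccinated children. If part of the baseline comes from malaria admissions, that part would tend to fall with malaria, for reasons unrelated to the safety of the vaccine.

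**Working it through.** No figure in the plan tests this point, and the study-size tables do not depend on it. The check is mainly a comparison of text.

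**1. Are secondary diagnoses counted?** SAP 7.2.3 and 7.2.8.1 both give them a date. A date of occurrence has no use in a rate unless the event can enter the numerator. So at least some secondary diagnoses are meant to count.

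**2. Does any SAP rule remove those from malaria admissions?**

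| Place | Unit | Effect on a secondary, non-malaria term in a malaria admission |
|---|---|---|
| Protocol 9.2.5.2 | Admission | Outside: the admission is due to malaria |
| SAP 6.9.2.2 | Coded event | Inside: the term is not an AESI, meningitis or malaria |
| SAP 7.2.3 | Coded event | Dated at admission |
| SAP 7.2.8.1 | Coded event | Merged only with the same preferred term on the same date or one day later, so it stays separate from the malaria event |
| SAP 9 | – | No change declared |

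The same gap applies when the primary diagnosis is an AESI or meningitis.

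**3. Is there a concrete route?** One is in the documents. Protocol Annex 5 confirms a generalised seizure as an AESI only after severe malaria, among other causes, has been excluded. SAP 7.2.7 foresees the code R56.0 being entered in the other-AE section. A convulsion during a malaria admission can therefore be recorded there.

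**4. Dating.** For a secondary diagnosis the admission date stands in for onset. With windows of 7 and 30 days, a condition that began before a dose counts as inside if the admission falls in the window. A condition that began inside counts as outside if the admission comes later.

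**5. Size, as illustration only.** Let m be the share of admissions due to malaria and s the mean number of qualifying secondary diagnoses per malaria admission. Take one event per non-malaria admission, and ignore AESI and meningitis admissions. Per N admissions the protocol rule gives (1−m)N events and the SAP rule gives (1−m)N + msN, so

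count ratio (SAP/protocol) = 1 + ms/(1−m).

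The documents give neither m nor s. Assumed ranges are m = 0.2 to 0.6 and s = 0.1 to 0.5.

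| m | s | Calculation | Count ratio | Share of counted events from malaria admissions, 1 − 1/ratio |
|---|---|---|---|---|
| 0.2 | 0.1 | 1 + 0.02/0.8 | 1.025 | 2% |
| 0.4 | 0.3 | 1 + 0.12/0.6 | 1.20 | 17% |
| 0.6 | 0.5 | 1 + 0.30/0.4 | 1.75 | 43% |

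**6. Direction in the before-after comparison.** Let p be the share in the last column, R the true ratio for events from non-malaria admissions, and f the fraction by which malaria admissions fall. With s unchanged over time,

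observed ratio = (1−p)R + p(1−f) = R − p[R − (1−f)].

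Whenever R exceeds 1−f, which includes any true rise (R above 1), the observed ratio lies below R. The direction follows without a value for p or f; the size does not.

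**The case against.** The strongest reply is that the SAP never says in words that diagnoses coded during a malaria admission count. The sentence in 7.2.8.1 is a dating rule. SAP section 4 states that the endpoints are as per protocol, and a secondary diagnosis may equally belong to an admission whose primary diagnosis is another other AE, which protocol 9.2.5.2 allows. The protocol itself codes these events in MedDRA and counts subjects with at least one event. The programming specifications, coding guidelines and mock tables were not available and could contain a filter. All of this stands as a limit: the conclusion is a reading of SAP 6.9.2.2, 7.2.3 and 7.2.8.1 together. It does not remove the gap, because the SAP text that defines a co-primary endpoint should carry the exclusion, and it does not.

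A reader might infer four stronger points that the documents do not support.

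- **Only primary diagnoses should count.** Protocol 9.2.5.2 speaks of what the admission was due to and does not mention primary diagnosis. A primary-only rule would drop concurrent diagnoses in non-malaria admissions that the protocol does not exclude.
- **Malarial anaemia is being counted as an other AE.** SAP 6.9.2.2 mentions anaemia only to illustrate the merging of similar terms, and severe anaemia is a criterion within the severe malaria definition. Nothing shows that it is also coded separately.
- **Chronic secondary conditions are counted again at each readmission in the under-5 rate.** The rule in SAP 6.9.3.3 that counts all events is worded for a repeated AESI; extending it to other AEs is an inference.
- **A stated amount of masking.** One could take a 1.5-fold true rise, a 20% to 50% malaria share, and the protocol's trial efficacy of 34.9% (severe malaria, 30 months) or 45.1% (clinical malaria, 18 months). The observed ratio would run from 0.8 × 1.5 + 0.2 × 0.651 = 1.33 down to 0.5 × 1.5 + 0.5 × 0.549 = 1.02. The share and the 1.5 have no source. Efficacy over 18 or 30 months after dose 3 does not match 7- and 30-day windows after each dose. Nor does it match a whole-community rate that includes children who were not vaccinated.

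**Conclusion.** The concern holds for the hospitalisation part of the endpoint. Followed as written, the SAP lets non-malaria terms coded as secondary diagnoses in malaria admissions into a co-primary safety rate that the protocol restricts to other admissions, and it does not declare the difference. The same holds for secondary terms in AESI and meningitis admissions. Such events can also affect which 10 AE groups receive a post-vaccination rate, and they are placed in short windows by admission date. Events that are themselves malaria remain excluded, and the death part is not affected.

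The likely effect on the before-after comparison is downward. That rests on malaria falling after introduction, on unchanged coding practice, and on the same counting rule in EPI-MAL-003, whose plan was not available. The size is unknown. Count ratios of about 1.03 to 1.75 follow from assumed inputs and show only that the effect could be trivial or large.

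**What to change.** - In SAP 6.9.2.2, 7.2.3 and 7.2.8.1, for the hospitalisation component only, exclude events from admissions whose primary final diagnosis is an AESI, meningitis or malaria. Using the primary final diagnosis to represent what an admission was due to is an operational choice. It agrees with the protocol's definition of a malaria hospitalisation in 9.2.5.7 and with SAP Table 4.
- Tabulate the excluded secondary diagnoses in a separate descriptive table.
- Keep concurrent diagnoses in the remaining admissions, and add a sensitivity analysis restricted to primary diagnoses, which have an onset date.
- Leave the death component on contributing cause, as in protocol 9.2.5.8.
- If the sponsor keeps the broader count, list it in SAP section 9 and report the restricted rate beside it.

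The main filter needs no new data, because the main diagnosis is already recorded in the eCRF. The costs are SAP wording, one filter, one sensitivity analysis, lower counts per AE group and one extra table.

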#### **7.2.8.2. Malaria cases**

In the same way, to avoid counting the same malaria episode more than once, episodes in the same subject with a difference between admission dates for outpatient visit or between onset dates for hospitalised cases of  $\leq 14$  days and with the same specie(s) (identified either with rapid diagnostic test or slide reading), will be considered as one event. A worst case allocation is attributed according to the following order (starting from worst):

- Severe malaria (with the same species)
- Uncomplicated malaria (with the same species)
- Clinically diagnosed malaria
- Suspected malaria

*Remarks:*

1. In case two or more consecutive visits/hospitalisations, with less than 14 days between each visit and/or hospitalisation, only one event will be considered also (even if there is more than 14 days between the first and the last visit and/or hospitalisation).
2. Malaria episodes can only be combined if their outpatient visit admission date or their onset dates are complete.

#### **7.2.9. Definition of malaria cases**

*For final analysis, only malaria per protocol will be considered (i.e. uncomplicated and severe malaria, including cerebral malaria).*

##### **7.2.9.1. Uncomplicated malaria**

*Plasmodium* parasitaemia  $> 0$  detected by microscopy and/or RDT

AND

Presence of fever (temperature  $\geq 37.5^{\circ}\text{C}$ ), as reported by the parent(s)/LAR(s) or recorded at the time of presentation

OR

Occurring in a child who is unwell and brought for treatment to a health care facility.

AND

Without signs of severity or evidence (clinical or laboratory) of vital organ dysfunction.

#### 7.2.9.2. Severe *P. falciparum* malaria

Severe malaria was defined according to the following two definitions along the study:

Definition 1 [WHO, 2010]	Definition 2 [WHO, 2015], from protocol amendment 4

P. falciparum parasitaemia > 0 detected by microscopy and/or RDT
 
AND
 
One or more of the following, occurring in the absence of an identified alternative cause:
 
 
Impaired consciousness: a Blantyre coma score < 3 in children;
 
Prostration: generalised weakness so that the person is unable to sit, stand or walk without assistance;
 
Multiple convulsions: more than two episodes within 24 h;
 
Acidosis: a base deficit of > 8 mEq/L or, if not available, a plasma bicarbonate level of < 15 mmol/L or venous plasma lactate <math>\geq</math> 5 mmol/L. Severe acidosis manifests clinically as respiratory distress (rapid, deep, laboured breathing).
 
Hypoglycaemia: blood or plasma glucose < 2.2 mmol/L (< 40 mg/dL);
 
Severe malarial anaemia: haemoglobin concentration <math>\leq</math> 5 g/dL or a haematocrit of <math>\leq</math> 15% in children < 12 years of age with a parasite count > 10,000/<math>\mu</math>L;
 
Renal impairment: plasma or serum creatinine > 265 <math>\mu</math>mol/L (3 mg/dL) or blood urea > 20 mmol/L;
 
Jaundice: plasma or serum bilirubin > 50 <math>\mu</math>mol/L (3 mg/dL) with a parasite count > 100,000/<math>\mu</math>L;
 
	
P. falciparum parasitaemia > 0 detected by microscopy and/or RDT
 
AND
 
One or more of the following, occurring in the absence of an identified alternative cause:
 
 
Impaired consciousness: a Glasgow coma score < 11 in children <math>\geq</math> 2 years of age or a Blantyre coma score < 3 in children < 2 years of age;
 
Prostration: generalised weakness so that the person is unable to sit, stand or walk without assistance;
 
Multiple convulsions: more than two episodes within 24 h;
 
Acidosis: a base deficit of > 8 mEq/L or, if not available, a plasma bicarbonate level of < 15 mmol/L or venous plasma lactate <math>\geq</math> 5 mmol/L. Severe acidosis manifests clinically as respiratory distress (rapid, deep, laboured breathing).
 
Hypoglycaemia: blood or plasma glucose < 2.2 mmol/L (< 40 mg/dL);
 
Severe malarial anaemia: haemoglobin concentration <math>\leq</math> 5 g/dL or a haematocrit of <math>\leq</math> 15% in children < 12 years of age with a parasite count > 10,000/<math>\mu</math>L;
 
Renal impairment: plasma or serum creatinine > 265 <math>\mu</math>mol/L (3 mg/dL) or blood urea > 20 mmol/L;
 


Definition 1 [WHO, 2010]	Definition 2 [WHO, 2015], from protocol amendment 4

Pulmonary oedema: radiologically confirmed or oxygen saturation < 92% on room air with a respiratory rate > 30/min, often with chest indrawing and crepitations on auscultation;
 
Significant bleeding: including recurrent or prolonged bleeding from the nose, gums or venepuncture sites; haematemesis or melaena;
 
Shock: compensated shock is defined as capillary refill ≥ 3 s or temperature gradient on leg (mid to proximal limb), but no hypotension. Decompensated shock is defined as systolic blood pressure < 70 mm Hg in children, with evidence of impaired perfusion (cool peripheries or prolonged capillary refill);
 
Hyperparasitaemia: P. falciparum parasitaemia > 10%.
	
Jaundice: plasma or serum bilirubin > 50 µmol/L (3 mg/dL) with a parasite count > 100,000/µL;
 
Pulmonary oedema: radiologically confirmed or oxygen saturation < 92% on room air with a respiratory rate > 30/min, often with chest indrawing and crepitations on auscultation;
 
Significant bleeding: including recurrent or prolonged bleeding from the nose, gums or venepuncture sites; haematemesis or melaena;
 
Shock: compensated shock is defined as capillary refill ≥ 3 s or temperature gradient on leg (mid to proximal limb), but no hypotension. Decompensated shock is defined as systolic blood pressure < 70 mm Hg in children, with evidence of impaired perfusion (cool peripheries or prolonged capillary refill);
 
Hyperparasitaemia: P. falciparum parasitaemia > 10% (i.e. percentage of infected red blood cells > 10%; corresponding to > 500,000/µL).

#### 7.2.9.3. Severe *P. vivax* malaria

Severe *P. vivax* malaria is defined as for severe *P. falciparum* malaria when *P. vivax* parasitaemia > 0 detected by microscopy and/or RDT but with no parasite density thresholds.

#### 7.2.9.4. Cerebral malaria

Severe *P. falciparum* malaria with impaired consciousness (Glasgow coma score < 11 in children ≥ 2 years of age or Blantyre coma score < 3 in children < 2 years of age);

AND

If malaria with seizure: coma persisting for > 30 min after the seizure.

**7.2.10. Definition of anaemia**

Cases of anaemia will be defined as follow:

- All anaemia: haemoglobin <11g/dL.
- Severe anaemia: haemoglobin <7g/dL .

**7.2.11. Hospitalisation**

- Hospitalisations (all causes)
- Hospitalisation for malaria (including *P. falciparum* malaria)  
A hospitalised subject with malaria (including *P. falciparum* malaria)
- Hospitalisation for *P. falciparum* malaria  
A hospitalised subject with *P. falciparum* malaria

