9.2.5.6. Anaemia

- All anaemia: haemoglobin $< 11 \text{ g/dL}$ [[Stoltzfus, 1993](#)].
- Severe anaemia: haemoglobin $< 7 \text{ g/dL}$ [[Stoltzfus, 1993](#)].

CONFIDENTIAL115055 (EPI-MALARIA-002 VS AME)
Protocol Amendment 7 Final**9.2.5.7. Hospitalisation**

- Hospitalisations (all causes)
A subject requiring overnight stay in hospital/inpatient facility.
- Hospitalisation for malaria (including *P. falciparum* malaria)
A hospitalised subject with malaria (including *P. falciparum* malaria) and for whom malaria is the primary cause of hospitalisation.

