Malaria attributed hospitalisations	# of children hospitalised during study period where malaria is listed as the primary diagnosis Source: Hospitalisations	Person-years contribution of enrolled children

Incidence rates will be adjusted by means of Poisson regression models (the dependent variable will be the number of events). The details are given in Section 9.7.9.

Univariate and multivariable models will be conducted. Those adjusted covariates are described in Section 9.3.3:

- Study site.
- Demographic parameters such as age at reference date.

CONFIDENTIAL115055 (EPI-MALARIA-002 VS AME)
Protocol Amendment 7 Final

- Medical history and other risk factors such as chronic disease or diagnosed congenital disease, known HIV infection, malaria, malnutrition, drugs exposure, toxic agent exposure.
- Use of malaria control measures such as bednets, indoor residual spraying, seasonal malaria chemoprevention.
- Comorbidity factors such as premature birth, history of trauma.
- Health care seeking behaviour and distance to health care facilities.
- Type of health care facility.
- Neighbourhood of residence (urban/rural area).
- Total number of outpatient visits per centre.
- Seasonal MTI (i.e. parasite prevalence) estimated in study EPI-MAL-005 on the vaccine ineligible group (see [Annex 3](#) for definition).
- Other centre level covariates estimated in study EPI-MAL-005 per year: malaria control intervention use, bednet use and health care seeking behaviour.

The same strategy as described in Section [9.7.6.2](#) will be used for covariates selection to be included in the multivariable model.

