#### **6.10.5. Cause of hospitalisation (including AESI, other AE, meningitis and malaria) and death**

Causes of hospitalisation (including AESI, other AE, classified by MedDRA SOC and PT level as well as meningitis and malaria) will be analysed grouped as follows:

- Hospitalisations (all causes)
- Hospitalisation for malaria (including *P. falciparum* malaria)
- Hospitalisation for *P. falciparum* malaria

In the same way, descriptive analysis of causes of death classified by MedDRA will be done overall and by gender grouped as follows:

- Deaths – all cause
- Malaria attributed deaths (including *P. falciparum* malaria)
- *P. falciparum* malaria attributed deaths
- Deaths attributed to an AESI or other AE (i.e. other than meningitis, AESI, malaria)

Descriptive analysis of the cause of hospitalisation (overall) and death (overall and by gender) will consist in computing the number of cases, person-year per 100,000 and IR (with 95% CI).

IR of all cause of hospitalisation and death will be computed following EPI vaccine or virtual vaccination (at risk period of 12 months) as described in section [6.9.3.2](#) and for children < 5 years as described in section [6.9.3.3](#). Of note, death IR per gender in children < 5 years will be computed after the first year of recruitment. Indeed, census per gender will be available after the application on field on the Protocol Amendment 4.

Note that malaria subtype will be defined using outpatient and hospitalisation visits. In case of death occurring at home malaria subtype may be unknown.

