All cause hospitalisation	# of children hospitalised during the follow-up time of each analysis Source: Hospitalisations	Person-years contribution of enrolled children during the follow-up time of each analysis
Malaria attributable hospitalisation	# of children hospitalised during the follow-up time of each analysis where malaria is listed as the primary diagnosis Source: Hospitalisations	Person-years contribution of enrolled children during the follow-up time of each analysis
P. falciparum Malaria attributable hospitalisation	# of children hospitalised during the follow-up time of each analysis where P. falciparum malaria is listed as the primary diagnosis Source: Hospitalisations	Person-years contribution of enrolled children during the follow-up time of each analysis
Anaemia in hospitalised children	# cases of anaemia Source: Hospitalisations	Number of enrolled children
Severe anaemia in hospitalised children	# cases of severe anaemia Source: Hospitalisations	Number of enrolled children

As done for safety endpoints, analysis of risk factors will be conducted by means of univariate and multivariable Poisson regression models for ***any malaria, severe malaria and cerebral malaria***. The methods are described in Section 7.5.1. The covariates and their select method are described in Section 7.5.3.

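### SAP 7.2.11 drops the primary-cause condition from malaria hospitalisation, so one Table 5 endpoint could be counted under two definitions

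*SAP*

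**What the plan says.** Five places define or use malaria hospitalisation.

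- **Protocol 9.2.5.7** (case definition): a hospitalised child with malaria "and for whom malaria is the primary cause of hospitalisation". Protocol 9.3.2 ties the secondary endpoint to it: "see Section 9.2.5.7 for case definitions".
- **Protocol Table 8** (Section 9.7.7.2): the numerator is the number "of children hospitalised during study period where malaria is listed as the primary diagnosis".
- **SAP Table 4** (Section 6.11.2): the numerator is restricted to admissions "where malaria is listed as the primary diagnosis", and the *P. falciparum* row carries the same restriction.
- **SAP 7.2.11** (derived data): the whole rule is "A hospitalised subject with malaria", including *P. falciparum* malaria. The separate *P. falciparum* line is built the same way. Neither mentions primary cause or primary diagnosis.
- **SAP 6.10.5**: groups causes of hospitalisation under the 7.2.11 labels, including "Hospitalisation for malaria", and adds no condition of its own.

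SAP 4.2 presents the secondary endpoints as those of the protocol with added detail. Neither the SAP document history nor SAP Section 9 mentions a change to this definition.

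**The concern.** The omitted clause separates admission *for* malaria from admission *with* malaria. It matters here because the case definition of uncomplicated malaria is broad (protocol 9.2.5.5, SAP 7.2.9.1): any parasitaemia by rapid test or microscopy, plus fever or simply being unwell and brought for care, without signs of severity. A child admitted for another illness with a positive rapid test can meet it. The sites were chosen for moderate-to-high transmission, so such admissions are plausible.

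The protocol appears to draw the line on purpose. Malaria deaths need malaria only as a contributing cause (9.2.5.8), whereas malaria hospitalisations need it as the primary cause (9.2.5.7).

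At stake is whether some published malaria hospitalisation rates match the protocol's endpoint, and whether a reader of the report can tell which definition stands behind each figure.

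**Working it through.** The plan gives no figure to reproduce. The check is a comparison of texts, followed by the direction of the effect.

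**1. Is the condition present?**

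| Place | Primary cause or diagnosis required? |
|---|---|
| Protocol 9.2.5.7 | Yes |
| Protocol Table 8 | Yes |
| SAP Table 4, malaria row | Yes |
| SAP Table 4, *P. falciparum* row | Yes |
| SAP 7.2.11, malaria line | No |
| SAP 7.2.11, *P. falciparum* line | No |
| SAP 6.10.5 | Not stated; uses the 7.2.11 labels |

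**2. Which outputs could the gap reach?** SAP Table 5 gives each of the two malaria hospitalisation rows four quantitative outputs:

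- incidence following the primary and secondary schedules (6.10.5, with a 12-month risk period);
- incidence in children under 5 (6.10.5, by the method of 6.9.3.3);
- cumulative probability;
- incidence over the follow-up periods of 6.11.

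Only the last has its numerator fixed by Table 4. For the first three, the only definition in the SAP body is 7.2.11. One row of Table 5 therefore spans two written rules, and the SAP does not say which prevails.

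**3. Direction and size.** Dropping a condition can only add events. Let *f* be the share of events counted under 7.2.11 that would not count under the primary-cause rule. Then

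count under 7.2.11 ÷ count under the protocol rule = 1/(1 − *f*).

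The documents give no value of *f*. Purely as assumed inputs:

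- *f* = 5%: 1/0.95 = 1.05
- *f* = 10%: 1/0.90 = 1.11
- *f* = 30%: 1/0.70 = 1.43

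These show how the formula behaves and are not estimates. The unit of *f* also differs by output:

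- *Under-5 rates* count every event over census person-time (6.9.3.3). Here *f* is a share of admissions, and the rate scales exactly as the count.
- *Schedule rates* count the first event after each dose and stop follow-up there (6.9.3.2). A child with one primary-malaria admission in the window counts under either rule, so a share of admissions does not convert directly. Person-time would also shorten slightly, because the wider rule can end follow-up earlier.

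**4. Can the condition be applied?** Yes. Protocol 9.2.7.2.10 records main and secondary diagnoses separately, and SAP 7.2.3 already uses primary-diagnosis status to date other adverse events.

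**The case against.** The case on the other side is substantial.

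- **The impact analyses are safe.** A reader might infer that 7.2.11 dilutes the malaria endpoint used for vaccine impact. The documents do not support that. The analyses set up for comparison with EPI-MAL-003 are those of SAP 6.11, and Table 4 defines their numerators with the primary-diagnosis condition. This stands.
- **Two counts are possible, not shown.** A reader might infer that the report will certainly carry two definitions. But 6.10.5 does not cite 7.2.11, and its heading concerns the cause of hospitalisation. The 7.2.11 label itself says *for* malaria. The section may be a shortened copy of the protocol: its all-cause line has lost its definition too, and three lines in 7.2.12 have none. SAP 7.2 refers to separate programming specifications, which are not among these documents, so the coded filter cannot be seen. This stands as a limit on the claim, but it does not make the text right: the defining sentence as written omits the condition.
- **The rate sets differ anyway.** A reader might infer that the omission alone makes the rates impossible to reconcile. They already differ in window, population and counting unit: first event per dose in active surveillance, all events in both surveillances over census person-time, and dose-anchored periods in active surveillance only. This stands. The definition should still not be a further, unlabelled difference.
- **The endpoint is secondary and descriptive.** No co-primary endpoint, sample size or test depends on it. This stands and limits the weight of the point.

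**Conclusion.** The point holds in limited form. SAP 7.2.11 states a wider rule than protocol 9.2.5.7, for malaria and for *P. falciparum* malaria. It conflicts with protocol Table 8 and SAP Table 4, and it is undeclared although the SAP describes these endpoints as following the protocol. Protocol 9.7.4 requires departures from its statistical plan to be described and justified in the final report.

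If 7.2.11 is followed literally, the 6.10.5 schedule-based and under-5 rates and the Table 5 cumulative probabilities for malaria hospitalisation would include children admitted for another primary cause. The 6.11 rates keep the protocol's rule, provided Table 4 is followed as written. The bias would be upward, and its size cannot be derived from the documents.

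This is worth correcting before the final analysis because the text states a different rule, not merely an incomplete one. It is not evidence that the baseline for EPI-MAL-003 is compromised.

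**What to change.** In SAP 7.2.11, add to both the malaria and the *P. falciparum* definitions: "and for whom malaria is the primary cause of hospitalisation", with primary diagnosis given in brackets as the operational variable. This matches protocol 9.2.5.7 and SAP Table 4. Add a cross-reference to 7.2.11 in SAP 6.10.5 and Table 5, and confirm that the programming specifications apply the same filter.

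If admissions with malaria as any diagnosis are also of interest, report them as a separately labelled line and declare the addition in SAP Section 9.

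The cost is one clause in each of two definitions and one filter on data already collected.
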